#### *2.4.1.2 Case Control Study – Oncological treatments*

##### *Case Group*

Protocol V17 07.02.2023

- Identification of patients on the drug at the point of commencement of therapy
- Identification of patients admitted with a toxicity via tumour-group specific teams, acute triage logs, and real-time acute oncology on-line registry.
- Prospective patients that are attending irAEs $\geq$ grade 2 or endocrinopathies of any grade will be approached and assessed for eligibility both locally and nationally

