#### *Control Group*

- Cases and controls will be recruited in a 1:1 manner
- Only one group of controls (patients receiving the drug but not exhibiting toxicity) will be recruited for this section
- Controls will be required to be receiving treatments for a minimum period outlined in the eligibility section

Due to the very limited use of oncological immunotherapies in children, only adults will be recruited to this arm of the case control study.

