**4.1.2 Case-Control Study- Oncological treatments**

*Inclusion Criteria for Case-Control Studies*

Case (Age  $\geq$ 18 years):

- a. Subject is willing to take part
- b. 18 years of age or over
- c. Diagnosis of drug hypersensitivity, defined as any grade 2 irAE with a requirement for steroid treatment/ recurrence of symptoms/ >1 break in treatment OR grade 3/4 irAE, as per criteria laid out in the NCI CTCAE (v4) OR clinician decision OR an endocrinopathy of any NCI CTCAE grade
- d. Administration of at least one dose of either monotherapy or combination oncological treatment (including CPI, targeted treatments and chemotherapy)
- e. Any AE experienced up to 24 months after commencement of treatment
- f. Written informed consent obtained

*Control (Age  $\geq$ 18 years):*

Controls will be matched for age and duration of treatment to cases

- a. Participant willing to take part
- b. Currently taking oncological treatments without AE (grade 1 toxicity is acceptable)  
or

Protocol V17 07.02.2023

- c. Previously received oncological treatment, did not have >grade one toxicity and have stopped for reasons other than toxicity
- d. Ethnically matched to the index patient
- e. Written informed consent obtained

*Exclusion Criteria for Case-Control studies*

- a. Unwilling to take part
- b. Subject is unable to consent

Subject is, in the opinion of the investigator, not suitable to participate in the study

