### **5.3.2.2 Prospective skin arm (See 12.11)**

In addition to those patients experiencing skin toxicity and recruited at the time of toxicity, patients who are due to be commenced on a oncological treatment will be recruited to a prospective observational cohort study. They will be provided Prospective Punch Biopsy Patient Information Sheet. All visits and procedures shall take place either in out-patient Dermatology or Oncology

Protocol V17 07.02.2023

Clinics at experienced centres or established Clinical Research Units (CRU). Patients will be seen on two occasions by a trained health professional.

**Visit 1:** A representative 6mm punch biopsy will be taken from the patient's skin prior to treatment commencing. Furthermore, patients may also have a paired blood sample (up to 50mls) and plucked hair follicles (up to 20) taken.

**Visit 2:** A second review will be made within the first 4 weeks after treatment has been commenced at which point patients will be reviewed and a full skin examination performed. Patients will be grouped into those who develop skin reactions and those who do not. In those patients who develop a skin reaction, a 6mm punch biopsy will be taken from the affected skin in addition to a 6mm punch biopsy of the adjacent non-affected skin. If patients wish only to give a single punch biopsy then this will be taken from the involved skin. In patients who do not develop a skin reaction, a 6mm punch biopsy will be taken from a representative area of skin. In those patients who develop reactions involving the scalp we will ask the patient if they would be willing to have two smaller punch biopsies (up to 5mm) taken from the scalp in addition to normal skin (as above). In addition, 40mls of blood and up to 20 plucked hair follicles may be collected.

Should a patient develop a skin reaction subsequent to their follow up visit they will be offered the opportunity for a further skin biopsy (with paired blood sampling). As with the recruitment of patients at the point of toxicity a subsequent sample (with a paired blood sample) may be taken at the point of resolution.

At all points in skin sampling patients may be asked to complete a 5 minute questionnaire to assess the impact of their skin on their quality of life. This assessment is known as the Dermatology Life Quality Index Questionnaire (DLQI) and is a validated questionnaire used regularly in dermatology outpatient clinics. Clinical photographs may be taken at each time point.

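### In the oncology case-control study a grade 1 treatment-related endocrinopathy meets both the case and the control definition, and the minimum treatment period promised for controls is not given

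*Protocol*

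**What the plan says.** Case criterion c in Protocol 4.1.2 offers several routes to case status. They include certain grade 2 events, grade 3/4 events, clinician decision, and "OR an endocrinopathy of any NCI CTCAE grade". The case group in 2.4.1.2 carries the same rule: patients with irAEs of grade 2 or above "or endocrinopathies of any grade will be approached and assessed for eligibility". Case criterion d asks for a single dose, and criterion e sets the window: "Any AE experienced up to 24 months after commencement of treatment".

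On the control side of 4.1.2, criterion b reads "Currently taking oncological treatments without AE (grade 1 toxicity is acceptable"). Criterion c, the alternative for patients no longer on treatment, bars only toxicity above grade 1 and requires that treatment stopped for another reason. Controls are matched to cases on age and treatment duration and are also ethnically matched.

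Section 2.4.1.2 describes the controls differently: "Only one group of controls (patients receiving the drug but not exhibiting toxicity) will be recruited for this section". It adds: "Controls will be required to be receiving treatments for a minimum period outlined in the eligibility section". Appendix 3 (12.3) samples controls at a time point matched to cases and again at about day 84, even if the drug has been stopped for reasons other than toxicity.

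**The concern.** A case-control study needs case and control definitions that exclude each other. Here the case definition makes an exception for endocrinopathy, counting any grade, while the control definition has no matching exception and tolerates grade 1 toxicity of any kind. A true endocrine case can therefore sit in the comparison group.

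The protocol's stated interest is in immune, autoantibody and transcriptomic differences between patients with and without irAEs, and 5.3.3 singles out endocrinopathies as of special interest because they are irreversible. If some controls carry the event being studied, the measured difference for endocrine irAEs is pulled toward zero, and recruiting more patients under the same rules does not remove that bias.

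The absent minimum treatment period adds to this. It is the one rule in the protocol that would stop a patient being labelled a control after very little exposure, and the section it points to does not contain it.

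**Working it through.** **1. Can one patient meet both definitions?** Take a patient on treatment whose only toxicity is a grade 1 endocrinopathy caused by it, within 24 months of starting.

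- Case criterion c: met, because any grade counts. Criteria d (one dose) and e (24 months) are also met.
- Control criterion b: met, because grade 1 toxicity is allowed without exception.
- If the patient has since stopped for another reason, control criterion c is met, because only toxicity above grade 1 is barred.
- Exclusion criteria in 4.1.2: unwillingness, inability to consent, and investigator's opinion of unsuitability. None decides between case and control.

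The overlap follows from the text alone. Section 2.4.1.2, where controls show no toxicity, is stricter than 4.1.2, so the two sections also disagree.

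**2. Is there a minimum treatment period?** Section 2.4.1.2 refers to the eligibility section. For controls, 4.1.2 contains only matching on duration, and no other section gives a period. Matching supplies no fixed floor, because a case needs only one dose and a control matched to an early case can be equally early.

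**3. Must controls be on treatment?** Section 2.4.1.2 implies yes. Criterion c in 4.1.2 and the day-84 sampling rule in Appendix 3 say no.

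**4. How large could the overlap be?** The initial target in 3.6 is 25 cases and 25 controls per drug. It cannot be reproduced, because no significance level, power, effect size or SD is given. Section 5.3.3 gives thyroid irAE incidence as 6-11% on PD-1 inhibitors and 15% on combination therapy.

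Expected affected controls = 25 × incidence:

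- 25 × 0.06 = 1.5
- 25 × 0.11 = 2.75
- 25 × 0.15 = 3.75

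This is a loose upper bound for thyroid events. The rates are given without a grade split although grade 2 and above is barred from controls, and the sum treats controls as a random draw of treated patients with none already taken as cases.

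**5. What would that do to power?** This is an illustration only. Assume two-sided alpha 0.05, 80% power, an unchanged SD, and a misclassified control with the same mean as the cases. The detectable standardised difference with 25 per group is (1.960 + 0.842) × √(2/25) = 0.79. A share f of misclassified controls leaves (1 − f) of the difference.

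| f | Difference left | Power |
|---|---|---|
| 0 | 0.79 | 80% |
| 0.06 | 0.74 | 75% |
| 0.11 | 0.71 | 70% |
| 0.15 | 0.67 | 66% |

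At f = 0.15, holding 80% power needs 25 / 0.85² = 34.6, so 35 per group. A grade 1 case milder than the average case would dilute less than this.

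**The case against.** The best defence is that the text shows what can happen, not what does. Section 2.4.1.2 says endocrinopathies of any grade are approached as cases and describes controls as free of toxicity, so recruiting staff may well assign such patients correctly. What is missing could be seen as one sentence on precedence. That stands as a limit on the size of the problem. It does not remove it, because 4.1.2 is the operative eligibility list and it allows both labels.

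Four stronger readings are tempting, and the documents do not support them.

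- **Future cases among controls.** A reader might infer that the grade 3/4 rates in 2.1 (5-30% on monotherapy, about 55% on combination) are the share of latent cases among controls. They are incidences among all treated patients. Controls with past toxicity above grade 1 are already barred, and nothing shows that a sample taken before an event resembles one taken during it.
- **Excluding later converters.** Controls are duration-matched and sampled at a matched time point. Under incidence-density sampling, an event-free control who later becomes a case is legitimate, and removing such controls selects on future information. The protocol does not declare that design, but it does not contradict it either.
- **The thyroid sub-study.** Section 5.3.3 samples patients with thyroid irAEs and defines no control group there. The overlap lies in the case-control study.
- **The prospective skin arm.** In 5.3.2.2, "Patients will be grouped into those who develop skin reactions and those who do not" might be read as fixing the analysis groups at four weeks. In context it determines which biopsies are taken at Visit 2, and later reactors are offered further sampling.

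**Conclusion.** The control criteria are wrong as written. A grade 1 endocrinopathy arising on treatment satisfies both definitions in 4.1.2, and the minimum treatment period cited in 2.4.1.2 does not exist in the eligibility section. The two sections also disagree on whether controls may have stopped treatment. These points rest on the text and need no outside figure.

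The consequence is possible misclassification, with bias toward zero in the endocrine part of the toxicity contrast to the extent that affected controls resemble cases. Its size cannot be derived from the protocol. The thyroid bound of about 1.5 to 3.75 of 25 controls is a ceiling under the assumptions shown, not an estimate; the power figures rest on an assumed alpha and target power. The protocol gives no rates for other endocrinopathies, so they are not covered by the bound.

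**What to change.** 1. Amend control criteria b and c in 4.1.2 so that the grade 1 allowance does not cover an endocrinopathy arising on the oncological treatment under study. No patient then meets both definitions by that route. Limit the wording to treatment-related events: a ban on all endocrinopathy would also remove controls with pre-existing endocrine disease while leaving such patients among the cases, which would distort the question of personal susceptibility.
2. Reconcile 2.4.1.2 with 4.1.2 on duration. Either require the control's treatment duration at sampling to be at least the matched case's duration at irAE onset, or delete the reference to a minimum period.
3. Align 2.4.1.2 with control criterion c and Appendix 3 on whether patients who have stopped treatment are eligible controls.
4. Record each control's toxicity status at the existing day-84 sample, and examine later converters in a sensitivity analysis. Keep them in the main contrast.

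The cost is an eligibility amendment and one status entry at a visit already planned. A few potential controls are lost or recruited as cases instead.

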### **Controls**

A single sample will be taken at a matched time point to cases and subsequent samples will be taken at the start of month 4 (~day 84) following the first sample (even if CPI has been discontinued on non-toxicity ground eg disease progression). Patients will have 40mls of blood taken at each visit and may have microbiome samples taken alongside. If control patients wish to contribute further to the study and give further blood samples at different durations of therapy for further matching this will be permitted.

We will not request that subjects donate more than 475mL of blood in a period of 16 weeks. This is the blood donation volume and rate adopted by the National Blood Service for England and Wales ([www.blood.co.uk](http://www.blood.co.uk)) and is thus a well recognised national standard.

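### Oncology controls are on treatment in one section and may have stopped it in another; time since last dose is not matched, so it can differ between cases and controls

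*Protocol*

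**What the plan says.** Three places in the protocol define the oncology controls.

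- **Section 2.4.1.2, Control Group.** "Only one group of controls (patients receiving the drug but not exhibiting toxicity) will be recruited for this section". The same list adds: "Controls will be required to be receiving treatments for a minimum period outlined in the eligibility section".
- **Section 4.1.2, Control.** The matching rule is "Controls will be matched for age and duration of treatment to cases", and a further criterion requires ethnic matching to the index patient. Criterion (b) covers patients on treatment with at most grade 1 toxicity. Criterion (c), joined to (b) by an explicit 'or', covers those off treatment: earlier recipients with nothing above grade 1 toxicity who "have stopped for reasons other than toxicity". The section gives no minimum treatment period and no maximum time since the last dose.
- **Appendix 3, Controls.** "A single sample will be taken at a matched time point to cases". Later control samples are taken "even if CPI has been discontinued on non-toxicity ground eg disease progression". The matched time point is not defined.

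Section 3.8 says that case-control data will be pooled with the prospective data to model dose against immune-related toxicity. Section 3.6 gives an initial target of 25 cases and 25 controls per drug.

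**The concern.** Sections 2.4.1.2 and 4.1.2 cannot both be followed. A site working from the first would recruit only patients on treatment, and a site working from the second could also recruit patients who stopped long ago. The minimum period that 2.4.1.2 refers to is missing from the section it points to.

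The statistical consequence concerns exposure at the time of sampling. The endpoints in section 3.7 include immune responses to the suspect drug, such as cytokines, surface markers and antibodies, and section 3.8 adds plasma drug levels. Some of these plausibly depend on whether drug is still present. Case sampling is tied to the toxicity, ideally before steroids and otherwise within 7 days of starting them (Appendix 3). Stopped controls have no comparable anchor. If the groups differ in time off drug, the contrast mixes toxicity with current exposure, and recruiting more patients does not remove that.

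**Working it through.** **Step 1: does the stated matching control time off drug?** Let D be the duration of treatment and S the time from first dose to sample. With continuous treatment, time off drug is S − D. Section 4.1.2 matches D. A control treated for as long as the case may have stopped a week or a year before sampling; D is the same and S − D is not. Matching D alone is therefore not enough.

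**Step 2: does Appendix 3 close the gap?** If the matched time point means time since first dose, S is matched as well, and S − D is matched implicitly when treatment has no breaks. If it means time on therapy, it only repeats D. The text does not say which. The same Appendix 3 paragraph mentions further control samples at other durations of therapy for additional matching, which points to the second meaning. The question stays open.

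**Step 3: are cases necessarily on drug?** No. Section 4.1.2 requires only one dose, accepts events up to 24 months after the start, and lists more than one break in treatment among the qualifying features of a grade 2 event.

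**Step 4: illustrative size.** The protocol gives no significance level, effect size or SD for this comparison, so there is no plan figure to reproduce. Assumptions, none of them from the protocol: two-sided 5% test, no true case-control difference, and a marker shifted by 0.5 SD in patients off drug.

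Spurious difference in SD units: b = 0.5 × (share of controls off drug − share of cases off drug).

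False-positive rate with n per group: P(|Z + b/√(2/n)| > 1.96).

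Section 3.6 supplies n = 25. It also caps recruitment at 100 patients per drug, and 1:1 recruitment (section 2.4.1.2) then gives n = 100/2 = 50.

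| Controls off drug | Cases off drug | b | n = 25 | n = 50 |
|---|---|---|---|---|
| 20% | 0% | 0.5 × 0.2 = 0.1 | b/√(2/25) = 0.35; 6.4% | b/√(2/50) = 0.5; 7.9% |
| 40% | 0% | 0.5 × 0.4 = 0.2 | 0.71; 10.9% | 1.0; 17.0% |
| 40% | 40% | 0 | 0; 5% | 0; 5% |

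A simulation of the two-sample t-test at n = 25 (20,000 runs) agrees: 6.5%, 10.4% and 4.8% for the three rows. With 40% of controls and 20% of cases off drug, it gives 6.5%.

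The result is sensitive to the assumed shift. At 1.0 SD with no case off drug, the simulated rates at n = 25 are 10% (20% of controls off drug) and 26% (40%).

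**The case against.** The strongest reply has four parts.

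- **The matched time point may already deal with it.** On one reading of Appendix 3 (step 2), time off drug is matched implicitly, and a control long off drug could be paired only with a similar case. Appendix 3 also plans openly for samples after discontinuation, so 2.4.1.2 may be loose shorthand. This stands in part: the gap is an undefined term rather than a proven absence of matching. But an undefined term protects nothing, and sites can read it differently.
- **Cases may be off drug too.** This stands. A reader might infer that drug washout *is* confounded with control status. The documents support only that it *can* be, because bias needs an imbalance between the groups.
- **The direction is unknown.** A reader might also infer that stopped controls look immunologically quieter and so mimic the expected case-control difference. The protocol does not support this. Cases may already be on steroids, and Appendix 3 names disease progression as a reason for controls to stop; either could move markers.
- **Part of this belongs in an analysis plan, and part of the data may be collected.** The oncology assessment takes a therapeutic history, and Appendix 7 lists dose and duration. But no last-dose date is named, and one not captured at sampling may be hard to recover. The handling of unmatched controls in the analysis can go in the SAP. Who is eligible, what is matched and what is recorded are protocol matters.

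**Conclusion.** The contradiction between sections 2.4.1.2 and 4.1.2 is plain on the text, and the promised minimum treatment period is absent. Time since last dose is not a stated matching factor, and the one phrase that might cover it is undefined. Time off drug can therefore differ between cases and controls and can confound exposure-dependent markers and the dose-toxicity model.

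Size and direction depend on an imbalance that the protocol does not let us estimate. Under the stated assumptions the illustration gives about 6% to 11% false positives at 25 per group and 8% to 17% at 50 per group, against a nominal 5%. There is no inflation when the off-drug shares are equal and the shift is the same in both groups.

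A reader might take 100 per group from the general target of 100 cases, for which the same formula gives up to 29%. The oncology sentence in section 3.6 caps patients, not cases, at 100 per drug, so with 1:1 recruitment that figure should not be relied on.

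This should be corrected. It does not show that the case-control comparison is invalid.

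**What to change.** 1. Reconcile section 2.4.1.2, section 4.1.2 and Appendix 3 on whether off-treatment controls are allowed. Either state the minimum treatment period or delete the reference to it.
2. Define the matched time point: state the event it is counted from and the permitted window.
3. Record the date of last dose before each sample for cases and controls.
4. If stopped controls are kept, match them to the index case on time from last dose to sample, or adjust for that time. Use those who cannot be matched only in a sensitivity analysis; this last part may sit in the SAP.

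The cost is one date field and one more matching factor, with no added procedure for participants. The downside is somewhat fewer controls in the main contrast, and some index cases may be harder to match.

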**4.1.3 Cohort Study – Drug Class NOS**

*Inclusion Criteria for Cohort Studies*

- a. Subject is willing to take part
- b. 18 years or over
- c. Subject is willing to donate “pre-dose” blood sample(s) and follow specified sampling regime
- d. Subject is being administered the drug

*Exclusion Criteria for Cohort Studies*

- a. Unwilling to take part
- b. Subject is unable to consent
- c. Subject is, in the opinion of the Investigator, not suitable to participate in the study

**4.1.4 Cohort Study – Oncological Immunotherapy**

*Inclusion Criteria for Adult Cohort Study*

- a. Subject is willing to take part
- b. 18 years or over
- c. Subject is willing to donate “pre-dose” blood sample (s) and follow a specified sampling regime
- d. Subject is being administered the drug

*Exclusion Criteria for the Adult Cohort Study*

- a. Unwilling to take part
- b. Subject is unable to consent
- c. Subject is, in the opinion of the investigator, not suitable to participate in the study

Protocol V17 07.02.2023

## 4.2 Patient Recruitment

### 4.2.1 Recruitment target

At present, we are unable to provide a total sample size of patients to be recruited. Given the different adverse drug reactions and the different frequencies at which they occur, it is not possible to give an exact number. However, given the rarity of some of the reactions, in most cases it will be unlikely that we will recruit more than 100 cases per culprit drug. Our general target will be 100 cases for each reaction. It is, therefore, vital we recruit patients both locally and nationally.

As we are unable to state the exact number of patients to be recruited, we will provide figures for the number of patients recruited following an ADR for all the drugs that are studied to the ethics committee in the annual report.

